### 9.1.7 Data handling and record keeping

To enable evaluations and/or audits from regulatory authorities or PTC Therapeutics, the investigator agrees to keep accurate and complete records, including the identity of all participating subjects (sufficient information to link eCRFs and clinic records/source documents), all original signed informed consent forms, electronic copies (ie, CD-ROM, USB, etc.) or paper copies of the data that have been captured in the Electronic Data Capture (EDC) for each subject (eCRFs), and detailed records of study drug disposition. All records and documents pertaining to the study will be maintained by the investigator until notification is received from PTC Therapeutics that the records no longer need to be retained.

The investigator must obtain written permission from PTC Therapeutics before disposing of any records. The investigator will promptly notify PTC Therapeutics in the event of accidental loss or destruction of any study records. If the investigator relocates, retires, or for any reason withdraws from the study, the study records may be transferred to an acceptable designee, such as another investigator, another institution, or to PTC Therapeutics as applicable.

### 9.1.8 Protocol deviations

A protocol deviation is defined as any intentional or unintentional change to, or noncompliance with, the approved protocol procedures or requirements. Deviations may result from the action or inaction of the subject, investigator, or site staff. Examples of deviations include, but are not limited to:

- Failure to adhere to study exclusion and inclusion criteria
- Failure to comply with dispensing or dosing requirements
- Use of medications that are specifically prohibited in the protocol
- Missed or out-of-window visits
- Drug dosing not administered within the time frame specified in the protocol
- Failure to adhere to test requirements, including vital signs, laboratory tests, physical examinations, PK blood draws, medical history, etc. – either tests not done, incorrect tests done, or not done within the time frame specified in the protocol
- Procedural deviations such as incorrect storage of study drug, failure to update the ICF when new risks become known, or failure to obtain IRB approvals for the protocol and ICF revisions

Significant deviations are any deviations that impact subject eligibility (ie, protocol inclusion/exclusion violations), subject safety or a subject's ability to continue in the clinical trial.

At the outset of the study, a process for defining and handling protocol deviations will be established with the CRO. This will include determining which deviations will be designated significant; thus, requiring immediate notification to the PTC Therapeutics medical monitor and the sponsor.

Prospective deviations (eg, protocol waivers) are prohibited per PTC policy.

The investigator is responsible for seeing that any known protocol deviations are recorded handled as agreed.

### **9.1.9 Publication and data sharing policy**

The information developed during the conduct of this clinical study is considered confidential by PTC Therapeutics. This information may be disclosed as deemed necessary by PTC Therapeutics.

PTC Therapeutics intends that the data from this study will be presented and published. The PTC Therapeutics staff under the direction of the PTC Therapeutics Chief Medical Officer or designee in collaboration with the investigator will be responsible for writing presentations and manuscripts for publication. Investigators will not be allowed to publish or present the data from this study without prior agreement with PTC Therapeutics.

The investigator is obliged to provide the sponsor with complete test results and all data derived by the investigator from the study. During the study, only the sponsor may make study information available to other study Investigators or to regulatory agencies, except as required by law or regulation. Except as otherwise allowable in the clinical study site agreement, any public disclosure (including publicly accessible websites) related to the protocol or study results, other than study recruitment materials and/or advertisements, is the sole responsibility of the Sponsor.

The sponsor may publish any data and information from the study (including data and information generated by the investigator) without the consent of the Investigator. Manuscript authorship for any peer-reviewed publication will appropriately reflect contributions to the production and review of the document. All publications and presentations must be prepared in accordance with this section and the Clinical Study Site Agreement. In the event of any discrepancy between the protocol and the Clinical Study Site Agreement, the Clinical Study Site Agreement will prevail.

Data from all sites participating in the study will be pooled and analyzed by the sponsor or the sponsor's designee. The first publication of the study results shall be made in conjunction with the results from other study sites as a multicenter publication. If a multicenter publication is not forthcoming within 24 months of completion of the study at all sites, the Investigator may publish or present the results generated at his or her site.

The investigator will provide the sponsor with a copy of any proposed publication or presentation for review and comment at least 60 days prior to such presentation or submission for publication. The sponsor shall inform the investigator in writing of any

changes or deletions in such presentation or publication required to protect the sponsor's confidential and proprietary technical information and to address inaccurate data or inappropriate interpretations in the context of any pooled multicenter results. At the expiration of such 60-day period, the investigator may proceed with the presentation or submission for publication unless the sponsor has notified the institution or the investigator in writing that such proposed publication or presentation discloses the sponsor's confidential and proprietary technical information. Further, upon the request of the sponsor, the investigator will delay the publication or presentation for an additional 90 days to permit the sponsor to take necessary actions to protect its intellectual property interests.

## 9.2 Additional Considerations

Not applicable

## 9.3 Protocol Amendment History

Amendment 1: 22 Oct 2018 (Version 2.0)

Amendment 2: 06 May 2019 (Version 3.0)

**The overall reason for the amendment:** The overall reason for the amendment was to ensure that sufficient muscle tissue for analysis was obtained from the biopsy procedure, to extend the screening window, to add information on concomitant use of corticosteroids and cardiac drugs for cardiomyopathy prophylaxis/treatment, to update the exploratory PK assessments and analyses, and to update the ataluren dosing table.

Item No.	Protocol Section	Amendment/Update	Reason/Rationale
1	Synopsis and Sec 2.2.3	Exploratory endpoints: deleted specific PK parameters	Allow for analysis of other parameters
2	Synopsis, Sec 3.1.1, and Sec 3.2 Bullet #2	Revised from █ muscle biopsy samples to up to approximately 450 mg of muscle tissue (up to █ cores per muscle); allowed sample from the █ muscle if obtained sample is not evaluable for analysis	To ensure sufficient muscle tissue for analysis
3	Synopsis Table 1 and Sec 7 Table 1	Extended screening window from 30 to 45 days; added details for assessing height/weight and physical exams, deleted details of PK analyses	Increase visit window; clarification
4	<del>Section 3.1.4</del>	Information on PK analyses moved to Section 8.4.4	Clarification
5	Section 4.1	Added text on homogeneity of study population	Clarification
6	Section 6.2	Added that drug will be administered with food.	Clarification
7	Section 6.4.1	Added information on Corticosteroids	Clarification
8	Section 6.4.4	Added information on Cardiac Drugs for Cardiomyopathy Prophylaxis/Treatment	Concomitant use of cardiac drugs for cardiomyopathy prophylaxis/treatment
9	Section 7.2	Added text and table on renal functioning and monitoring parameters	Safety precautions

**PTC124-GD-045-DMD**  
**Clinical Protocol**

Item No.	Protocol Section	Amendment/Update	Reason/Rationale
10	Sec 7.3.8, Table 5	Deleted: Exposure during pregnancy or breastfeeding”	Clarification
11	Section 7.3.9	Deleted: “This information is also provided in the Study Manual and in the SAE report form.” Deleted telephone number for SAE reporting.	Clarification
12	Section 8.4.2	Added: “The dystrophin level will be summarized by muscle biopsy locations using descriptive statistics.”	Clarification
13	Section 8.4.4	Added information on PK analyses	Clarification
14	Section 8.4.5	Added information on safety evaluations	Clarification
15	Section 9.3	Added Protocol Amendment History	Update
16	Appendix	Added dosing table	Update
17	Synopsis and Protocol	Document date/version, abbreviations and references were updated; small grammatical changes were made throughout.	Update

**11 APPENDIX**

PTC124-GD-045-DMD Dosing Table

## LIST OF ABBREVIATIONS AND DEFINITIONS OF TERMS

Abbreviation or Specialized Term	Explanation
AE	Adverse event
CK	Creatine kinase
COVID-19	Coronavirus disease of 2019
CRF	Case report form
CV	Coefficients of variability
ECL	Electrochemiluminescence
eCRF	Electronic case report form
IHC	Immunohistochemistry
ITT	Intent-to-treat
LLOQ	Lower limit of quantification
MedDRA	Medical Dictionary for Regulatory Activities
MMRM	Mixed effect model repeated measurement
N	Number of subjects
nmDMD	Nonsense mutation Duchenne muscular dystrophy
PK	Pharmacokinetics
PP	Per protocol
% normal	Percentage of the predicted levels
PT	Preferred term
rNSAA	Revised North Star Ambulatory Assessment
SAE	Serious adverse event
SAP	Statistical Analysis Plan
SOC	System organ class
TFT	Timed function test
TEAE	Treatment-emergent adverse event

## 1. INTRODUCTION

The purpose of this Statistical Analysis Plan (SAP) is to describe the procedures and the statistical methods that will be used in analyzing and reporting results for study PTC124-GD-045-DMD (hereafter referred to as Study 045). This SAP is prepared based on the study protocol V3.0 (dated 06May2019). The reader is referred to the study protocol, the electronic case report form (eCRF), general eCRF completion guidelines, and various data collection instruments employed in the study for details of study design, conduct and data collection.

## 2. STUDY DESIGN

[figure not shown]
This is an open-label, single-arm, Phase 2 study designed to evaluate the ability of ataluren treatment to increase dystrophin protein levels in muscle cells of patients with nonsense mutation Duchenne muscular dystrophy (nmDMD). The study will evaluate the levels of dystrophin before and after 40 weeks of ataluren therapy using muscle biopsies and two validated assay methods.

Approximately, 15 to 20 ataluren-naïve male subjects, aged  $\geq 2$  and  $< 8$  years of age will be administered ataluren.

Ataluren will be dosed daily 10 mg/kg in the morning, 10 mg/kg at midday, and 20 mg/kg in the evening (10, 10, 20 mg/kg).

The study will have a screening visit and 3 additional visits (Figure 1). At the screening visit, which will be performed at a patient's local site, inclusion/exclusion criteria, demographics and medical history will be assessed. In addition, blood will be drawn for genotyping to confirm that a subject carries a nonsense mutation in the dystrophin gene. For all subjects, Visit 1 and Visit 3 will occur at the same site, that of [REDACTED]. During Visit 1 and Visit 3 biopsies will be performed and used for assessing dystrophin protein levels. At Visit 1, the first dose of ataluren will be administered following the biopsy at [REDACTED] and subjects, parent/caregivers or legal guardian will be dispensed a supply of ataluren which will be administered at home. Visit 2 will be in the clinic at the subjects' local site and weight will be measured to determine if the dose of ataluren requires adjustment. Adverse events (AE), serious adverse events (SAE), concomitant medications, and compliance will also be captured, and an additional supply of ataluren will be dispensed.

**Figure 1: Study Schematic**

No interim analysis will be conducted for this study.

### **3. STUDY OBJECTIVES AND ENDPOINTS**

#### **3.1. Study Objectives**

##### **3.1.1. Primary Objective**

To assess the change in levels of dystrophin in ambulatory nmDMD subjects after treatment with ataluren for 40 weeks using quantitative assay, such as electrochemiluminescence (ECL).

##### **3.1.2. Secondary Objective**

To assess dystrophin levels/intensity and protein localization by immunohistochemistry (IHC).

##### **3.1.3. Exploratory Objectives**

The exploratory objectives are as follows:

- To assess the change from baseline in revised North Star Ambulatory Assessment (rNSAA) and timed function tests (TFTs) after 40 weeks of ataluren treatment
- To assess changes from baseline in creatine kinase (CK) levels after 40 weeks for ataluren treatment
- To evaluate the steady state pharmacokinetics (PK) of ataluren after 40 weeks of treatment

#### **3.2. Study Endpoints**

##### **3.2.1. Primary Endpoint**

The percent change from baseline in dystrophin levels (final concentration) following 40 weeks of ataluren therapy, as measured by an ECL-based immunoassay that has been validated and will be run under Good Laboratory Practice conditions.

##### **3.2.2. Secondary Endpoint**

The percent change in dystrophin levels (mean membrane stain density) from baseline after 40 weeks of ataluren therapy as determined by a validated IHC assay.

##### **3.2.3. Exploratory Endpoints**

The exploratory endpoints are as follows:

- Change from baseline in rNSAA after 40 weeks of treatment
- Change from baseline in TFTs after 40 weeks of treatment
- Change from baseline in CK levels after 40 weeks of treatment
- PK assessments at Week 1 and Week 40

### 3.3. Sample Size Determination

Approximately, 15 to 20 ataluren-naïve male subjects, aged  $\geq 2$  and  $< 8$  years of age is planned to be enrolled in this study. Limited information is available about the magnitude and intra-subject variability of the change in dystrophin levels, as measured by an immunoassay such as ECL following 40 weeks ataluren therapy in this patient population. Assuming a baseline dystrophin level of 0.2% of control levels (as per previous dystrophin replacement therapy [Center for Drug Evaluation and research Application number: 206488Orig1s000 Eteplirsen Summary Review]), Table 1 shows the number of subjects needed to achieve an 85% power to detect an increase from baseline in dystrophin of 0.04%, 0.06% and 0.08%, for intra-subject coefficients of variability ranging from 20% to 35%, using a one-sided test at alpha 5%. As an example, if the increase from baseline is 0.08% and the intra-subject coefficient is 30%, 13 evaluable subjects would be required to have a power of 85% to detect this increase.

**Table 1: Summary of number of subjects required to achieve 85% power to detect increase in dystrophin levels from baseline**

Increase of dystrophin from baseline	Intra Subject CV			
	20%	25%	30%	35%
0.04%	19	29	41	55
0.06%	10	15	21	28
0.08%	7	10	13	18

**Abbreviations:** CV, coefficients of variability

## 4. STUDY POPULATIONS

### 4.1. Screened Population

Screened population is defined as all patients who have signed informed consent.

### 4.2. Enrolled Population

Enrolled population is defined as the subset of screen population who are not screen failures.

### 4.3. Intent-to-Treat Population

This analysis set will include all enrolled subjects with treatment assignments. In addition, subjects in this analysis set must have a valid assessment of dystrophin levels at baseline, as measured by ECL. This analysis set will be used for the primary endpoint analyses and summaries of other efficacy endpoints.

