### 7.1. Primary Efficacy Analyses

#### 7.1.1. Primary Analysis

The primary efficacy endpoint is the percent change from baseline in dystrophin levels (final concentration) following 40 weeks of ataluren therapy, as measured by ECL. The final concentration is calculated by dividing a sample's dystrophin concentration by its total protein concentration. In addition, the percentage of the predicted levels (% normal) will also be calculated as dystrophin levels normalized to dystrophin concentration of the control population ([Syneos Health Report No. 14597.051619.A](#)):

$$\% \text{ normal (in \%)} = 100 * \text{final concentration} / 33.8$$

Within each muscle location, the best, median, and the average of the dystrophin levels and the corresponding % normal values of the muscle cores will be summarized using descriptive statistics for each subject. In case any measured dystrophin concentrations are below the lower limit of quantification (LLOQ), the dystrophin concentrations will be set at 0.5\*LLOQ in the final concentration calculation for the statistical analysis.

The null hypothesis of the primary analysis is that the percent change from baseline in dystrophin levels following 40 weeks of ataluren therapy as measured by ECL is zero with the alternative hypothesis being that the change is greater than zero. To evaluate this hypothesis, a one-sided test at the 5% significance level will be employed.

The percent change from baseline at Week 40 in dystrophin levels measured by ECL will be analyzed using the mixed effect model repeated measurement (MMRM) analysis with factors of muscle locations, visits (baseline and Week 40) as fixed effects, and subjects as a random effect, based on ITT population. An unstructured covariance matrix will be used, and if the model fails to converge, then a compound symmetry matrix will be used. Since dystrophin level is known to be non-normally distributed, a log-transformation will be used in the analysis. The best dystrophin levels across all muscles are considered the primary analysis. A sample SAS code of the MMRM model is provided as follows:

```
proc mixed data = dataset;  
  
class subjid visit mlocation; /*mlocation is muscle location*/  
  
model lnaval = visit mlocation; /*lnaval is log-transformed dystrophin level*/  
  
random subjid;  
  
repeated visit / type = un;  
  
estimate "Week 40 change from baseline" visit -1 1;  
  
run;
```

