## 7.2. Secondary Efficacy Analyses

### 7.2.1. Secondary Efficacy Analysis

The secondary efficacy endpoint is the percent change from baseline in dystrophin levels (mean membrane stain density) after 40 weeks of ataluren therapy as determined by a validated IHC assay. Within each muscle location, the best, median, and the average dystrophin levels of the muscle cores will be summarized using descriptive statistics for each subject. The secondary efficacy endpoint will be analyzed using the same method as described in Section 7.1.1 (Primary Analysis). The best dystrophin levels across all muscles are considered the primary interest. As supportive analyses, the average and median dystrophin levels across all muscles, and subgroup analyses of the best, median, and mean dystrophin levels within each muscle location will be considered. In addition to dystrophin levels (the mean staining intensity), the percentage of positive fibers will also be summarized using descriptive statistics.

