### 7.2.2. Sensitivity Analyses

The following analyses will be considered as sensitivity analyses for the secondary efficacy endpoint:

- PP analysis: The same secondary efficacy analysis described in Section 7.2.1 (Secondary Analysis) will be repeated based on PP population for the secondary efficacy endpoint.
- The average and median dystrophin levels (mean membrane stain density) across all muscle locations will be analyzed using the same analysis method as described in Section 7.2.1 (Secondary Analysis).
- Excluding subjects with baseline dystrophin levels [REDACTED] of the predicted levels: The same analysis described in Section 7.2.1 (Secondary Analysis) will be repeated excluding subjects with baseline dystrophin levels [REDACTED] of the predicted levels. The same analysis on the average and median dystrophin levels across all muscle locations will also be repeated excluding such subjects.
- Subgroup analysis: The subgroup analysis by muscle location will be performed on secondary efficacy endpoint as described in Section 7.1.2 (Subgroup Analyses).
- COVID-19 considerations: The Week 40 study day (defined as Week 40 biopsy date – first study drug date +1) will be added to the efficacy analysis model described in Section 7.2.1 (Secondary Analysis) as a covariate. This analysis model will be applied to the best, average, and median dystrophin levels analyses based on the ITT population.

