### 7.3. Exploratory Analyses

No hypothesis testing will be performed on all exploratory endpoints. All exploratory endpoints will be summarized using descriptive statistics based on ITT population.

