#### 7.3.1. Revised North Star Ambulatory Assessment

The rNSAA consists of 17 activities, each scored as 0, 1, or 2. The sum of the 16 activities (exclude head lift) will form a total score. If fewer than 13 of the 16 activities are performed, the total score will be considered missing. If from 13 to 16 activities are performed, the total score will be standardized as follows:

$$\text{Standardized total score} = \frac{\text{observed total score}}{\text{number of non-missing activities}} \times 16$$

Transformation of the total score into a linear scale ([Mayhew 2013a](#)) will also be performed.

The mean and mean change from baseline in the total score and its linear transformation will be summarized at the Baseline and Week 40 visits based on ITT population. In addition, the proportion of subjects who has lost function after 40 weeks of ataluren treatment, defined as a drop of score from 1 or 2 at baseline to a score of 0 at the Week 40 visit, will be tabulated for each activity.

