## **9. PHARMACOKINETIC BLOOD SAMPLE**

The PK assessments using sparse sampling and population PK modeling will be presented in a separate report. The mean, median, minimum, maximum, %CV and geometric mean of plasma concentration at pre-dose and post-dose at each visit will be summarized based on the ITT population. In case any measured plasma concentrations are below LLOQ, the plasma concentrations will be set as 0 in calculations for the statistical analysis.

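### Because ITT membership requires a valid baseline ECL value, a treated child without one drops out of the IHC, function, CK and plasma-concentration summaries, none of which depend on ECL

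*SAP*

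**What the plan says.** SAP Section 4.3 defines the ITT set as enrolled subjects with a treatment assignment and adds that "subjects in this analysis set must have a valid assessment of dystrophin levels at baseline, as measured by ECL". It gives the set a wide use: "This analysis set will be used for the primary endpoint analyses and summaries of other efficacy endpoints". Protocol Section 8.3.1 has the same definition and the same use.

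Later sections tie each non-ECL measure to this set:

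- **IHC (secondary).** SAP 7.2.1 states: "The secondary efficacy endpoint will be analyzed using the same method as described in Section 7.1.1 (Primary Analysis"). The model in 7.1.1 has "subjects as a random effect, based on ITT population". The COVID-19 sensitivity analysis of IHC in 7.2.2 names the set outright: it is to "be applied to the best, average, and median dystrophin levels analyses based on the ITT population".
- **Exploratory endpoints.** SAP 7.3: "All exploratory endpoints will be summarized using descriptive statistics based on ITT population". For rNSAA, 7.3.1 repeats that the scores "will be summarized at the Baseline and Week 40 visits based on ITT population". Sections 7.3.2 (timed tests) and 7.3.3 (CK) do likewise.
- **Plasma concentrations.** SAP 9: pre-dose and post-dose values "will be summarized based on the ITT population".

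**The concern.** A baseline ECL value is a natural entry condition for an analysis of change in ECL dystrophin. It has no bearing on whether a child's stair climb, CK or plasma concentration can be summarised, and IHC has its own baseline. Under the rule as written, one failed laboratory assessment removes a treated child from five other summaries.

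Two features add to this. Protocol Section 1.3 justifies the use of two assays partly because together they make it more likely that each biopsy gives an interpretable result. Making entry to the IHC analysis depend on ECL success gives some of that benefit away. Also, protocol Section 6.3 has the baseline and Week 40 biopsies assayed together. Whether a child counts for function, CK and plasma concentration is therefore settled by an assay run after those data have been collected.

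At stake is avoidable loss of information in a trial of 15 to 20 children. The validity of the primary result is not in question.

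**Working it through.** **1. Does any other set recover the child?** The SAP defines these sets:

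| Set | SAP section | Recovers a treated child without valid baseline ECL? |
|---|---|---|
| Screened, Enrolled | 4.1, 4.2 | Not assigned to any of these endpoints |
| ITT | 4.3 | No, by definition |
| Per protocol | 4.4 | No, it is a subset of ITT |
| Safety | 4.5 | Yes, but used for safety summaries only |

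The safety outputs do not help for CK, because SAP 8.2 excludes it from all laboratory summaries and listings. The by-subject listings in SAP 5.1 cover selected eCRF domains and may still show some of the other data.

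**2. What triggers the exclusion?** A result below the LLOQ does not, because SAP 7.1.1 sets it to 0.5 × LLOQ. SAP 7 provides for multiple samples from each core, and for a substitute muscle when a sample is not evaluable. So the whole child must lack a valid baseline ECL result. The SAP does not define a valid assessment, nor say whether one evaluable core or muscle is enough.

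**3. The plan's own sizing figure.** SAP 3.3 gives 13 evaluable subjects for an increase of 0.08% from 0.2% at CV 30%, 85% power and one-sided 5%. A paired t-test on the log scale, with difference ln(0.28/0.20) = 0.336 and SD √2 × 0.30 = 0.424, returns 13. The figure reproduces, but it concerns ECL and this point does not rest on it.

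**4. Size per child lost.** With planned N of 15 to 20 (SAP 3.3):

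- Share of subjects: 1/20 = 5.0%; 1/15 = 6.7%.
- 90% interval half-width, taken as t(0.95, n−1) × SD/√n with SD unchanged:
  - 20 to 19: (1.734/√19) / (1.729/√20) = 0.3978/0.3866 = 1.03
  - 15 to 14: (1.771/√14) / (1.761/√15) = 0.4733/0.4547 = 1.04

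This is a simple paired-interval approximation to the planned mixed model. It applies to IHC only, which inherits the two-sided 90% interval of SAP 7.1.1. SAP 7.3 allows no hypothesis testing for rNSAA, timed tests and CK, and SAP 9 lists only descriptive statistics for concentrations.

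**5. How often?** The documents give no failure rate. For an assumed per-child rate p, the expected number lost is N × p and the chance of losing at least one child is 1 − (1 − p)^N:

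| Assumed p | N = 15: expected; chance of at least one | N = 20: expected; chance of at least one |
|---|---|---|
| 1% | 0.15; 14% | 0.2; 18% |
| 2% | 0.3; 26% | 0.4; 33% |
| 5% | 0.75; 54% | 1.0; 64% |
| 10% | 1.5; 79% | 2.0; 88% |
| 20% | 3.0; 97% | 4.0; 99% |

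The 1% row corresponds to an assumed 10% failure per muscle, two muscles failing independently (0.10 × 0.10). Correlated failure would raise it; the substitute muscle would lower it. Given step 2, the lower rows look too pessimistic.

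**The case against.** The strongest defence is that the trigger is remote and a common set is a reasonable choice. Whole-child ECL failure is unlikely under this biopsy scheme, and the failure rates above are assumptions. IHC is analysed only if the ECL endpoint is significant (SAP 5.5), so keeping both assays, function and concentrations on the same children has some logic. IHC also draws on the same biopsy material, so tissue too poor for ECL may fail IHC as well. All of this stands as a limit on size. It does not explain why a dosed child's CK, timed tests or plasma concentrations should be dropped, and the SAP does not give the common-set rationale.

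A reader might infer more than the documents support:

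- **That confidence intervals widen for every affected endpoint.** Of these, only IHC has a planned interval.
- **That the child is lost to all PK work.** SAP 9 sends population PK modelling to a separate report and does not state its population. Only the concentration summary is demonstrably restricted.
- **That the SAP anticipates ECL failures**, because Sections 6.1, 6.2 and 6.4 allow for ITT and safety sets that differ. That is conditional wording about which tables to print. It does not mention ECL, and the sets can differ for other reasons, since one needs a treatment assignment and the other a dose.
- **That the rule biases results.** Nothing shows this. Protocol 6.3 blinds assay staff to the timing of sample collection.
- **That the protocol expects frequent tissue failure.** Protocol 3.2 notes the difficulty and then lists the measures taken against it.

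**Conclusion.** The point holds on the text. As written, a treated child with no valid baseline ECL result leaves the IHC, rNSAA, timed-test, CK and plasma-concentration summaries even with complete data, and CK then has no planned summary at all.

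The effect is small and of unknown frequency, possibly nil. It is limited to a 3-4% wider IHC interval per child lost, where that child's IHC is itself usable, and to a smaller n in the descriptive summaries. The interval figure assumes an unchanged SD and one child lost from 15 or 20. The ECL analysis is unaffected, and the ECL condition is sensible there. This is a worthwhile tidy-up, not a flaw that threatens the conclusions.

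**What to change.** Keep the baseline ECL condition for the ECL endpoint only. Then define the other sets by their own data:

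- **IHC:** treated subjects with a valid baseline IHC value.
- **rNSAA, timed tests, CK:** treated subjects with a valid baseline for that measure.
- **Plasma-concentration summary:** dosed subjects with a PK sample.

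This needs wording in SAP 4.3, 7.2, 7.3 and 9. It also needs an entry in SAP Section 10, because protocol 8.3.1 contains the same definition and the change departs from it. While 4.3 is open, say what counts as a valid assessment and whether one evaluable core or muscle is enough.

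No new data are needed. The cost is that the denominator varies by endpoint and the endpoints are no longer all summarised on one common set of children. The summary tables already report n (SAP 5.1), so the difference will be visible.
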